### 11.5. Country-Specific Requirements

Country-specific requirements are provided in separate country-specific protocol.

---

## 11.6. Protocol Amendment History

The Protocol Amendment Summary of Changes Table for the current amendment is located directly before the Table of Contents (TOC).

### 11.6.1. Amended Protocol 01

Primary changes:

- Updated clinical development status text to account for a patient death, which was reported in a patient with cerebral venous sinus thrombosis (CVST) in the ALN-AT3SC-002 study (Phase 1/2 open-label extension study)
- Additional safety measures were implemented to mitigate risk of thrombosis in the lowered-AT setting, including: revised bleed management guidelines to allow standard BPA regimens only up to the first 7 days following fitusiran dosing; added recommendations for monitoring and management of thrombotic events; added clarification of definitions for bleeding episodes; revised recommendations for management of sepsis, and adding additional exploratory laboratory assessments
- Frequency of directed physical exams to monthly
- Updated Benefit-Risk Assessment section accordingly with respect to the above new safety monitoring
- Added Patient Education Module training to Schedule of Assessments
- Clarification added that Adverse Events should include review for signs and symptoms of thrombosis at each visit
- Clarifications added to the Perioperative Schedule of Assessments
- Addition of acetaminophen restriction to <4 grams per day
- Stipulation added that antifibrinolytics may be used as single agents, but may not be used in combination with factor or BPA
- Addition that aPCC and rFVIIa are not recommended for use as combination therapy
- Revised bleed management recommendations following discontinuation of fitusiran; standard on-demand dosing with BPAs is permitted when AT residual activity level returns to ~60% (per the central laboratory)
- Addition of prothrombin activation fragment 1,2 to the coagulation panel, as exploratory marker of hemostasis
- Addition of new stipulation for patients who present to the study site for management of bleed symptoms, samples will be collected pre-treatment and post-treatment with factor or BPA for the exploratory purposes of characterizing thrombin generation and other coagulation parameters
- Other minor corrections applied.

TSQM	Treatment Satisfaction Questionnaire for Medication
TSS	transformed scale score
VR	ventricular rate
WHO	World Health Organization

1 INTRODUCTION

Hemophilia A and hemophilia B are X-linked recessive inherited bleeding disorders, characterized by deficiency of coagulation factor (F) VIII or FIX, leading to a profound defect in the generation of thrombin leading to impaired hemostasis and increased risk of bleeding. Antithrombin (AT) is a natural anticoagulant expressed in the liver that plays a key role in inhibiting thrombin. Furthermore, AT acts as an inhibitor of FVIIa and FXa, which are typically at normal levels in patients with hemophilia A or B. Extensive preclinical in vitro and in vivo studies have described that a reduction of AT may be a potential safe and effective way to correct the generation of thrombin in both hemophilia A and B and control against microvascular and macrovascular traumatic bleeding episodes. Therefore, suppressing the production of AT is being investigated as a potential treatment for hemophilia.

Patients who develop inhibitory antibodies to FVIII or FIX represent a distinct subset of the population with hemophilia. These patients typically sustain more difficult-to-treat bleeding episodes, resulting in increased morbidity and increased mortality. A treatment that can effectively and safely prevent or reduce the frequency of bleeding episodes in patients with hemophilia A or B, including those with inhibitors, may reduce treatment burden, improve clinical outcomes and enhance quality of life.

Fitusiran is an investigational agent, comprising a synthetic siRNA covalently linked to a triantennary GalNAc ligand, designed to suppress liver production of AT as a strategy to rebalance the hemostatic system, thereby improving the generation of thrombin and hemostasis in individuals with hemophilia.

In the ATLAS-INH study (ALN-AT3SC-003 [EFC14768]), fitusiran is evaluated as prophylaxis to prevent or reduce the frequency of bleeding episodes in patients with hemophilia A or B who have inhibitory antibodies to FVIII or FIX and are being treated with on-demand bypassing agents. This statistical analysis plan (SAP) contains definitions of analysis populations and endpoints, outlines the timing of statistical analyses, and provides a comprehensive description of statistical analyses to be implemented to assess the clinical efficacy and safety of Study ALN-AT3SC-003 (EFC14768), protocol amendment 1 (referred to as Global Protocol hereafter) and United States amendment 1 (referred to as US Protocol hereafter), both dated 09 November 2017, and protocol amendment 2 dated 27 June 2018. The contents of this SAP will apply to both versions of protocol amendment 1 and amendment 2 unless otherwise specified, where the methodologies for the two versions of protocol amendment 1 are discussed separately. The data analyses will be used for the Clinical Study Report.

2 STUDY OVERVIEW

2.1 Synopsis of Study Design

[figure not shown]
ALN-AT3SC-003(EFC14768) is a multicenter, multinational, randomized, open-label Phase 3 study designed to evaluate the efficacy and safety of fitusiran in male patients aged ≥ 12 years with hemophilia A or B, with inhibitory antibodies to FVIII or FIX, who are not receiving prophylactic therapy.

Eligible patients will be randomized in a 2:1 ratio to:

- **Fitusiran treatment arm:** Fitusiran 80 mg administered SC as prophylaxis once monthly, with use of on-demand bypassing agent for treatment of breakthrough bleeding episodes
- **On-demand arm:** On-demand bypassing agent (BPA) for treatment of breakthrough bleeding episodes

The study design schema is presented in [Figure 1](#).

Figure 1: Study Design

Abbreviations: BPA = bypassing agent; HA/HB = hemophilia type A / hemophilia type B; R = randomized

^aOn-demand local BPA as routinely prescribed by physician per local standard practice.

^bFitusiran treatment arm patients who do not enroll in the extension study: AT activity level will be monitored at monthly intervals until returning to activity levels return to approximately 60% (per the central laboratory) or per Investigator discretion in consultation with the study Medical Monitor.

2.2 Randomization Methodology

Patients are randomized 2:1 to the fitusiran treatment arm and the on-demand arm. Randomization is stratified by the number of bleeding episodes in the 6 months prior to Screening (≤ 10 vs > 10).

2.3 Unblinding

Although this is an open-label study, Sponsor personnel will not have access to efficacy summaries by treatment arms prior to conducting the formal reporting of the study.

2.4 Study Procedures

The schedule of assessments is described in the study protocol (Table 1).

2.5 Modifications to the Statistical Section of the Protocol

This section summarizes major changes to the protocol statistical section. These changes are made before the first patient is randomized. The statistical analysis plan history table below gives the timing, rationale, and key details for major changes to the protocol statistical section.

The first patient was enrolled on February 14, 2018. There are no planned interim analyses.

Protocol Amendment statistical changes

Amendment number	Date approved	Rationale	Description of statistical changes
1	09-Nov-2017	Revised the definition of efficacy period based on on-treatment strategy for the primary analysis of primary endpoint in assessing the primary objective of the study (ICH E9 (R1)).	Efficacy period (Day 29 to Day 246) defined in the protocol is changed to (Day 29, earliest of (Day 246, or the last day of bleeding follow up), excluding the period for each intercurrent event.
1	09-Nov-2017	Added exclusion periods due to fitusiran treatment discontinuation, major or minor surgery, prophylactic treatment with emicizumab or factor since including bleeding events in these periods in the primary analysis would bias fitusiran treatment effect.	Exclusion period for each intercurrent event is described in details in Section 6.3

[figure not shown]
[figure not shown]
2.6 Statistical Modifications Made in the Statistical Analysis Plan

[figure not shown]
This section summarizes major changes in statistical analysis features made in approved SAP versions from statistical considerations in protocol or previous SAP versions, with emphasis on changes after study start (after the first patient was enrolled). These changes are made before database lock.

The statistical analysis plan history table below gives the timing, rationale, and key details for major changes to the statistical analysis features in the statistical analysis plan.

Statistical analysis plan statistical changes

SAP version number	Date approved	Rationale	Description of statistical changes
2	20-Jul-2019		The sensitivity analysis to include all bleeding events was added in Section 6.3.1.2.
2	20-Jul-2019		The summary statistics for number of patients who lost-to-follow-up and who had each intercurrent event is added in Section 6.3
2	20-Jul-2019		A summary of missing data pattern by treatment arm for patient who doesn't have bleeding data after Day 28 is added in Section 6.3.1.1. A sensitivity analysis based on imputed bleeding data in the efficacy period using multiple imputation (MI) method is added in Section 6.3.1.1.
2	20-Jul-2019		A sensitivity analysis based on zero-inflated negative binomial model is added in Section 6.3.1.2.

SAP version number	Date approved	Rationale	Description of statistical changes
2	20-Jul-2019	To be aligned with protocol amendment 02	The secondary endpoint 'Change in Haem-A-QOL scores in the treatment period' is changed to 'Change in Haem-A-QOL physical health score and total score in the treatment period' in Section 3.2.1 and Section 5.7. The analysis of physical health score is added in Section 6.3.2.4.
2	20-Jul-2019	To clarify how to calculate domain score when item scores are missing for Haem-A-QOL and Haemo-QOL assessments.	The method to calculate domain score when item scores are missing for Haem-A-QOL and Haemo-QOL assessments is added in Section 8.1.
2	20-Jul-2019		For the change in Haem-A-QOL physical health score and total score, the examination of normality assumption based on ANCOVA model and sensitivity analysis based on the non-parametric Wilcoxon-Mann-Whitney test are added in Section 6.3.2.4. In addition, a sensitivity analysis to handle missing assessment is also specified in Section 6.3.2.4.
2	20-Jul-2019	To clarify ANCOVA analysis for Haemo-QOL for small sample size	Clarify that only the descriptive statistics will be provided if ANCOVA model does not converge due to small sample size in Section 6.3.3.4.
2	20-Jul-2019		An exploratory analysis to evaluate the association between the change in Haem-A-QOL physical health and total scores and ABR and concomitant pain medication use is added in Section 6.3.2.4.

SAP version number	Date approved	Rationale	Description of statistical changes
2	20-Jul-2019		An exploratory analysis of bleeding symptoms is added in Section 6.3.1.3.
2	20-Jul-2019	To be aligned with protocol amendment 02	'Adverse events of clinical interest (AECI)' is changed to 'Adverse events of special interest (AESI)' throughout. Systemic injection associated reactions (IARs) is added to the criteria of AESI in Section 6.6.2.
2	20-Jul-2019	To be aligned with Sanofi's standard analysis for Lab and vital sign.	Lab analysis by NCI CTCAE grade and shift tables are removed in Section 6.6.3 since PCSA analysis will be performed. Vital sign by PCSA is added in Section 6.6.4.
2	20-Jul-2019	To align the analysis reference date with Day 1 visit date when baseline assessments are done, fitusiran first dose is given, and eDiary is distributed to the patients.	The reference date is changed from randomization to Day 1 visit date in Section 5.2. The baseline definition is changed from randomization to Day 1 visit in Section 5.5.
2	20-Jul-2019	To define geographic regions	Geographic regions are defined in Section 5.11.
2	20-Jul-2019	AT lowering capacity of fitusiran is expected to achieve therapeutic target range at the end of the onset period for the 80 mg fixed dose. ABR by AT lowering analysis does not add much value to the ABR comparison between onset period and efficacy period.	The analysis of ABR by AT lowering in Section 6.4.3 is removed.

SAP version number	Date approved	Rationale	Description of statistical changes
2	20-Jul-2019	In addition to the primary analysis of ABR for the recurrence of events, it is also of interest to compare the time to first bleeding event between on-demand treatment and fitusiran prophylaxis treatment.	The exploratory analysis of time to first bleeding event is added in Section 6.3.1.3
2	20-Jul-2019	To include untreated bleed in the bleeding episode definition	The untreated bleed is included in the bleeding episode definition in Section 6.3.
3	This version	To update Per-protocol Analysis Set definition	The detail deviations are included in the Per-protocol analysis set definition in Section 4.
3	This version	To define Covid-19 Unaffected Set	Covid-19 Unaffected Set is defined in Section 4.
3	This version	To clarify baseline definition for fitusiran group	For fitusiran group only, baseline definition is changed from Day 1 to first dose date in Section 5.5
3	This version	To clarify the multiplicity adjustment for Haem-A-QOL endpoints	For the two Haem-A-QOL scores (physical health score and total score), physical score will be tested first followed by total score.
3	This version	To add patient disposition category for Covid-19 impact summary	Patients discontinue the treatment due to Covid-19 and patient discontinue the study due to Covid-19 are added in Section 6.1
3	This version	Due to the exclusion criteria 6, the analysis of fibroscan/fibrotest result at baseline against worst post-baseline ALT elevation is not necessary	The related analysis is removed in Section 6.6.3

SAP version number	Date approved	Rationale	Description of statistical changes
3	This version	To add the efficacy analyses for ABR endpoints due to Covid-19 impact	For ABR, the sensitivity analyses on Covid-19 unaffected set is added in Section 6.3. In addition, a sensitivity analysis to exclude the bleeds during the period of missing at least 2 consecutive doses due to Covid-19 event is added in Section 6.3.
3	This version	To add the analyses for Haem-A-QoL due to Covid-19 impact	For sensitivity analyses, ANCOVA model will be run on Covid-19 unaffected set, on the set excluding data collected with Covid-19 impact, on the set of patients whose responses level to EQ-5D dimensions “anxiety/depression” is no change or improved from baseline.
3	This version	To add the sensitivity analysis for Haem-A-QoL baseline assessments	For sensitivity analyses, the same analysis as main but excluding values of those who completed Haem-A-QoL at baseline on the same day but after first dose of fitusiran.
3	This version	To add the AE summary related to Covid-19 infection	AE potentially consistent with COVID-19 will be summarized by SOC and PT and list will also be provided. The search term list is added in the Appendix 8.2
3	This version	To add AE summary by hemophilia type	By hemophilia type summary is added to key AE tables.

3 OBJECTIVES AND ENDPOINTS

3.1 Objectives

3.1.1 Primary Objective

- To evaluate the efficacy of fitusiran compared to on-demand treatment with bypassing agents, as determined by the frequency of bleeding episodes.

3.1.2 Secondary Objectives

- To evaluate the efficacy of fitusiran compared to on-demand treatment with bypassing agents, as determined by:
 - The frequency of spontaneous bleeding episodes
 - The frequency of joint bleeding episodes
 - Health-related quality of life (HRQOL) in patients ≥ 17 years of age
- To determine the frequency of bleeding episodes during the onset period
- To determine the safety and tolerability of fitusiran

3.1.3 Exploratory Objectives

- To evaluate the effects of fitusiran as compared to on-demand treatment with bypassing agents on the following patient reported outcomes:
 - Patient satisfaction with treatment
 - Patient activity
 - HRQOL in adolescents (≥ 12 to < 17 years of age)
- To determine the pharmacodynamic (PD) effect, pharmacokinetics (PK), and immunogenicity of fitusiran
- To evaluate the effects of fitusiran as compared to on-demand treatment with bypassing agents on the total weight-adjusted consumption of bypassing agents
- To evaluate the effects of fitusiran as compared to on-demand treatment with bypassing agents on joint status
- To evaluate the effects of fitusiran as compared to on-demand treatment with bypassing agents on patient resource use

3.2 Endpoints

3.2.1 Efficacy Endpoints

Primary and secondary endpoints for Global and US protocols are in the table below.

	Global Protocol	US Protocol
Primary	Annualized Bleeding Rate (ABR) in the efficacy period	ABR in the treatment period
Secondary	ABR in the treatment period	ABR in the efficacy period
	Annualized spontaneous bleeding rate in the efficacy period	
	Annualized joint bleeding rate in the efficacy period	
	Change in Haem-A-QOL physical health score and total score in the treatment period	
	ABR in the onset period	

Exploratory Efficacy Endpoints

- Change in the following in the treatment period:
 - Treatment Satisfaction Questionnaire for Medication (TSQM) domain scores
 - Haemophilia Activities List (HAL) score
 - Paediatric HAL (pedHAL) score
 - EuroQOL-5 dimension (EQ-5D) score
 - Haemo-QOL score
 - Hemophilia Joint Health Score (HJHS)
- Number of target joint bleeding episodes
- Annualized weight-adjusted consumption of bypassing agents
- Change in patient resource use (eg, work/school attendance, visits to doctor/hospital)

3.2.2 Pharmacokinetic Endpoints

- All patients
 - Plasma PK parameters will be estimated using a population PK approach. The population PK analysis will be described in a separate population PK analysis plan
- Patients from East Asian sites only
 - In addition to population PK analysis, plasma PK parameters for the patients from the East Asian sites only will also be estimated using non-compartmental analysis. The plasma PK parameters will include, but may not be limited to:

- Maximum plasma concentration (C_{max})
- Time to maximum plasma concentration (t_{max})
- Elimination half-life ($t_{1/2\beta}$)
- Area under the concentration-time curve (AUC)
- Apparent clearance (CL/F)
- Apparent volume of distribution (V/F)
- Fitusiran levels in 0-24 h urine will be reported as cumulative amount of drug excreted unchanged in urine (A_e)
- Additional PK parameters for plasma and/or urine may also be calculated, if considered appropriate

3.2.3 Pharmacodynamic Endpoints

- AT activity level over time
- Thrombin generation over time

3.2.4 Safety Endpoints

- Adverse events
- Concomitant medications
- Clinical laboratory parameters
- Vital signs
- 12-lead ECGs
- Physical examinations

3.2.5 Anti-drug Antibody Endpoints

- Incidence and titer of antidrug antibodies to fitusiran in the fitusiran treatment arm

4 PATIENT POPULATION

The populations (analysis sets) are defined as follows:

- Intent-to-treat (ITT) Analysis Set: All randomized patients. All by-treatment analyses based on the ITT analysis set will be performed according to the randomized treatment arm. Efficacy Analyses will be conducted using the ITT Analysis Set unless otherwise specified.
- Safety Analysis Set: All patients who received at least 1 dose of study drug or were randomized to on-demand arm. All by-treatment analyses based on the safety analysis set will be according to the actual treatment received. Safety Analyses will be conducted using the Safety Analysis Set unless otherwise specified.
- Per-protocol Analysis Set: All patients in the ITT set who do not have protocol deviations in the following categories:
 - Failure to meet key Eligibility criteria, which will be identified prior to database lock
 - Actual treatment differs from IRS treatment assignment
 - Prophylactic use of BPA
 - Other protocol deviations that might significantly affect the completeness, accuracy, and/or reliability of the bleeding data.

The major or critical deviations to be considered are as follows.

- The subject is not male and/or is younger than 12 years, but the subject was randomized.
- The subject does not have severe hemophilia A or B with inhibitors as evidence by:
 - A laboratory FVIII level $<1\%$ or FIX level $\leq 2\%$ at Screening.
 - On-demand use of bypassing agents to manage bleeding episodes for at least the last 6 months prior to Screening, or meeting one of the following Nijmegen-modified Bethesda assay results criteria:
 - Inhibitor titer of ≥ 0.6 BU/mL at Screening,
 - Inhibitor titer of <0.6 BU/mL at Screening with medical record evidence of 2 consecutive titers ≥ 0.6 BU/mL,
 - Inhibitor titer of <0.6 BU/mL at Screening with medical record evidence of anamnestic response, but the subject was randomized.
- The subject does not have a minimum of 6 bleeding episodes requiring bypassing agent treatment within the last 6 months prior to Screening, but the subject was randomized.
- The subject has known co-existing bleeding disorders other than hemophilia A or B, but the subject was randomized.

- The subject currently uses bypassing agents as regularly administered prophylaxis designed to prevent spontaneous bleeding episodes, but subject was randomized.
 - The subject's actual treatment differs from randomization group.
 - Site provided incorrect stratification data in IRT for patient's randomization.
 - The subject initiated use of bypassing agents or other hemostatic agents as prophylaxis for bleeding episode prevention, including doses related to anticipated hemostatic challenges such as physical activity, during the treatment period but the study drug was not discontinued.
- PK Analysis Set: All patients who receive at least 1 dose of study drug and have evaluable PK data contributing to the estimation of PK parameters.
 - Operative Procedure Analysis Set: All patients who received at least one dose of study drug or were randomized to on-demand arm and underwent at least one operative procedure during the study.
 - Covid-19 Unaffected Set: All patients who had no major or critical protocol deviations due to Covid-19 at any visits up to end of study (Month 9).

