**Diagnosis and Main Eligibility Criteria**

This study will include males with severe hemophilia A or B with inhibitors, aged  $\geq 12$  years, who have had a minimum of 6 bleeding episodes requiring BPA treatment within the last 6 months prior to Screening. Diagnosis of severe hemophilia A or B will be based on a central laboratory measurement or documented medical record evidence of FVIII level  $< 1\%$  or FIX level  $\leq 2\%$  at Screening.

Patients with inhibitors must have used bypass agents on demand to manage bleeding episodes for at least the last 6 months prior to Screening and must meet one of the following Nijmegen-modified Bethesda assay results criteria: 1) Inhibitor titer of  $\geq 0.6$  BU/mL at Screening, OR 2) Inhibitor titer of  $< 0.6$  BU/mL at Screening with medical record evidence of 2 consecutive titers  $\geq 0.6$  BU/mL, OR 3) Inhibitor titer of  $< 0.6$  BU/mL at Screening with medical record evidence of anamnestic response.

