### 5. SELECTION AND WITHDRAWAL OF PATIENTS

#### 5.1. Inclusion Criteria

Each patient must meet all of the following inclusion criteria to be eligible for enrollment in the study:

1. Males  $\geq 12$  years of age.
2. Severe hemophilia A or B with inhibitors evidenced by:
  - a. A central laboratory measurement or documented medical record evidence of FVIII  $< 1\%$  or FIX level  $\leq 2\%$  at Screening.
  - b. On-demand use of BPAs to manage bleeding episodes for at least the last 6 months prior to Screening, and meet one of the following Nijmegen-modified Bethesda assay results criteria:
    - Inhibitor titer of  $\geq 0.6$  BU/mL at Screening, or
    - Inhibitor titer of  $< 0.6$  BU/mL at Screening with medical record evidence of 2 consecutive titers  $\geq 0.6$  BU/mL, or
    - Inhibitor titer of  $< 0.6$  BU/mL at Screening with medical record evidence of anamnestic response
3. A minimum of 6 bleeding episodes requiring BPA treatment within the last 6 months prior to Screening.

- 
4. Willing and able to comply with the study requirements and to provide written informed consent and assent in the case of patients under the age of legal consent, per local and national requirements.

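### The SAP's per-protocol deviation item for inclusion criterion 2 does not match the protocol: it has 'or' where the protocol has 'and', and it omits medical-record evidence of the factor level

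*SAP*

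**What the plan says.** Protocol Section 5.1, criterion 2a, allows two routes to establish the factor level: "A central laboratory measurement or documented medical record evidence of FVIII" (and the corresponding FIX threshold). Criterion 2b requires six months of on-demand BPA use "and meet one of the following Nijmegen-modified Bethesda assay results criteria". The synopsis, under the main eligibility criteria, agrees on both points: the patient must have used BPAs on demand "prior to Screening and must meet one of the following Nijmegen-modified Bethesda assay results criteria", and the diagnosis "will be based on a central laboratory measurement or documented medical record evidence of FVIII level".

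Protocol Section 8.2.1 defines the per-protocol set as intent-to-treat patients without major deviations and leaves those deviations to the SAP.

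SAP Section 4 first gives general exclusion categories, one of which is "Failure to meet key Eligibility criteria, which will be identified prior to database lock". It then gives a detailed list, introduced by "The major or critical deviations to be considered are as follows". One item covers a patient who lacks severe hemophilia with inhibitors as shown by two pieces of evidence. The first begins "A laboratory FVIII level", with the protocol's thresholds at Screening and no medical-record route. The second is on-demand use, "or meeting one of the following Nijmegen-modified Bethesda assay results criteria".

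SAP Section 2.6 records only that version 3 added the detailed deviations. Neither Section 2.5 nor Section 2.6 mentions or explains a change to criterion 2.

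**The concern.** The list helps decide who is in the per-protocol set, so it should be the complement of the eligibility rule it stands for. Here it differs from that rule in two places, and the differences pull in opposite directions. The connector *or* loosens the inhibitor requirement in a trial whose population is defined by inhibitors. Leaving out the medical record narrows the factor-level requirement.

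The per-protocol set is used for a repeat of the efficacy analysis (SAP Section 6.3.1.2) and for baseline tables (SAP Section 6.2). If the item can be programmed in more than one way, two programmers could build different sets from the same SAP. In an open-label trial it is better that membership rests on an exact criterion than on case-by-case judgement.

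**Working it through.** The plan gives no figure to reproduce. The check is one of logic.

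**Inputs.** Four yes/no conditions per patient:
- L: the screening laboratory factor level qualifies
- R: the medical record documents a qualifying factor level
- D: six months of on-demand BPA use
- T: at least one of the three titre criteria is met

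There are 2 × 2 × 2 × 2 = 16 profiles. They count logical combinations, not patients.

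**Protocol 5.1.** A patient satisfies criterion 2 if (L or R) and D and T. L or R holds in 3 of 4 combinations, and D and T in 1 of 4, so 3 × 1 = 3 profiles are eligible.

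**SAP item, plain reading.** The negative stands in the stem (the patient does not have the disease as evidenced by what follows) and the items below it are phrased positively. A patient is flagged if not [L and (D or T)].
- Ineligible but not flagged: L true, R either way (2), exactly one of D and T true (2), so 2 × 2 = 4 profiles. Two of them are patients treated on demand with no titre criterion met.
- Eligible but flagged: L false with R, D and T true, so 1 profile.

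**SAP item, *or* as a list of failures.** A patient is flagged if not L, or not D, or not T. No ineligible profile escapes, but the record-only eligible profile is still flagged.

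**SAP item, *a laboratory* taken to include a laboratory value in the record.** Replace L by (L or R). This assumes that record evidence is always such a value.
- With the plain *or*, 3 × 2 = 6 ineligible profiles escape and no eligible profile is flagged.
- With *or* as a list of failures, both counts are 0.

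| Reading of the item | Ineligible, not flagged | Eligible, flagged |
|---|---|---|
| Plain *or*; screening laboratory value only | 4 | 1 |
| List of failures; screening laboratory value only | 0 | 1 |
| Plain *or*; laboratory value in the record counts | 6 | 0 |
| List of failures; laboratory value in the record counts | 0 | 0 |
| Protocol wording restored | 0 | 0 |

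Only the reading that is generous on both points reproduces the protocol.

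**Other items in the list.** Current BPA prophylaxis is a separate deviation and catches some patients without D. No other item in the detailed list refers to the inhibitor titre.

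**Size per patient.** Protocol Section 1.3 plans 36 patients on fitusiran and 18 on demand. One misclassified patient is 1/36 = 2.8% or 1/18 = 5.6% of an arm.

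**The case against.** A reader might infer that the list does keep ineligible patients and does remove eligible ones. The documents do not support that as a statement of fact.

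- **The connector.** *Or* under a negative stem is common loose drafting for failing one thing or failing the other. On that reading no patient without a qualifying titre escapes. This stands as a possible reading. It is the less natural one, since a list of failures would ordinarily repeat the negative in its second half.
- **The factor level.** The SAP says *a laboratory*, not *a central laboratory*, and a factor level in the record will often be a laboratory result. The words *at Screening* do not exclude records, because the protocol attaches them to both routes. This also stands as possible. Against it, the SAP item keeps medical-record wording for two of the titre criteria and omits it for the factor level.
- **What counts as a deviation.** SAP Section 5.9 defines a protocol deviation as a departure from the design or procedures in the protocol. A patient enrolled on record evidence as the protocol permits has arguably departed from nothing. This is the strongest point against claiming that eligible patients are removed, and it is why the consequence is stated only as *could be flagged*.
- **Safety nets.** The key-eligibility category and the medical review before the primary analysis could catch a patient without an inhibitor. They may do so, but the SAP does not say which criteria are key.
- **Exposure.** Protocol Table 1 schedules FVIII/FIX levels at Screening without limiting them to a subset, and its notes say factor results are returned to confirm eligibility. The record route matters only for a patient whose screening value is missing or does not meet the threshold. This stands and suggests that few patients are exposed.

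**Conclusion.** The mismatch is real and unexplained: the SAP item departs from the protocol's criterion on the connector and on the accepted factor evidence. It is inconsistent and ambiguous wording, not a demonstrated misclassification. The plain-reading consequences depend on *or* making the two pieces of evidence alternatives and on *a laboratory* excluding the record. They also assume that the deviation review applies the list literally.

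A reader might also infer that the per-protocol analysis would fail to test the intended population. The documents do not show this, because they do not say how many patients qualified by record alone or lacked a qualifying titre. That number may be zero, and no effect on the rate ratio can be calculated. The primary efficacy analysis uses the intent-to-treat set (SAP Section 6.3.1.1), so the primary result, power and alpha are unaffected. This is a minor point, worth correcting because the correction is so simple.

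**What to change.** In SAP Section 4, replace the item with protocol inclusion criterion 2 copied word for word. The factor level is shown by central laboratory or documented medical record, and the patient has at least six months of on-demand use *and* one of the three inhibitor criteria. State that the deviation is failing 2a or failing 2b. The item is then the exact complement of the criterion, with no ineligible profile missed and no eligible profile flagged.

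Record the change in the SAP Section 2.6 table before database lock. The cost is SAP wording only: no protocol change, no new data and no change to the primary analysis.
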